5.3.1 Number of Participants

The sample size for the trial is based on the primary outcome of spontaneous vaginal delivery. Therefore, the sample size of $n=988$ (shared between Yale, Weill Cornell Medicine and Northwestern) is selected for this proposed study to detect a 10% absolute increase while accounting for an expected 5% attrition rate. We then estimate, on the basis of the sample size for the primary outcome, the power we will have to detect clinically significant differences in the secondary outcomes.

For the translational sub-study at Yale, we will seek consent to obtain plasma and urine from patients enrolled in the main study ($n=192$). In addition, plasma will be obtained from 48 patients in spontaneous labor.

For the milk collection sub-study at Yale and Weill Cornell Medicine, to detect a 10 mM difference in sodium concentration between the intrapartum nipple stimulation therapy group and the immediate synthetic oxytocin infusion group at 48 hours postpartum, with a standard deviation of 20 mM, 80% power, and a significance level of 0.05, a sample size of 32 participants per group is required. Accounting for an expected 30% dropout rate, we plan to recruit 46 participants per group.

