Milk samples will be collected up to twice a day. Antepartum milk samples (10 drops to up to ½ teaspoon) will be collected from individuals in the nipple stimulation group during the intrapartum phase. Samples will be collected every 12 hours until labor. Volume will be determined by the mothers based on the amount of milk produced and how much they want to use to feed the infant postpartum.

Postpartum milk samples will be collected from IV oxytocin and nipple stimulation treatments participants at approximately 12, 24, and 48 hours postpartum. At 12, 24 and 72 hours 6-10 drops of milk (or more if participant allows) will be collected to a sterile tube using a pump or manually expressed from the breast. At ~48 hours postpartum, we will aim to collect 0.5-2.5ml of milk to perform all the sodium and milk conductivity assays mentioned below. If mothers are still hospitalized at 72 hours, additional samples will be collected every 12 hours up to twice per day (6-10 drops).

0.5ml of milk is needed for analysis of Sodium and milk conductivity, 0.5ml of milk for RNA analysis and 1ml of milk for macronutrients analysis.

Biological samples will be collected and stored at Yale and Weill Cornell Medicine (WCM) under secure, temperature-controlled conditions before shipment to [name] lab in Ithaca. At collection time, all samples will be de-identified and labeled with unique study ID numbers and time since delivery, which contain no personally identifiable information. Yale and WCM sites will use REDCap to code and manage the associated clinical data and sample collection records. A secure, access-restricted linkage key connecting study IDs to patient identifiers will be maintained solely by the local research teams. [name] lab will only receive de-identified samples and coded data labeled with the study ID, and will have no access to patient identifiers. Results generated by [name] lab will be uploaded to the WCM REDCap database using the matched study IDs provided with the samples, ensuring

all data remain de-identified and participant confidentiality is maintained throughout the study.

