6.4.2 Sample Size Considerations

1) Total sample size for the trial: The sample size for the trial is based on the primary outcome of spontaneous vaginal delivery. Therefore, the sample size of n=988 is selected for this proposed study to detect a 10% absolute increase while accounting for an expected 5% attrition rate. We then estimate, on the basis of the sample size for the primary outcome, the power we will have to detect clinically significant differences in the secondary outcomes.

Sample size estimation for primary outcome:

Detectable absolute difference	Anticipated with nipple stimulation therapy	Total Sample size Across 2 Study Groups for 90% power
15%	79%	426
14%	78%	492
13%	77%	574
12%	76%	676
11%	75%	812
10%	74%	988
9%	73%	1,222

All sample size and power estimates are based on two-tailed tests. *This is important because we will be powered to detect both increases and decreases in outcomes with intrapartum nipple stimulation therapy (intervention) versus immediate synthetic oxytocin infusion without nipple stimulation (comparator).* The expected rate of spontaneous vaginal delivery in the setting of immediate synthetic oxytocin infusion without nipple stimulation used for the sample size estimation is based on averaged institutional data from the study sites. We estimate that a total of **988** (494 nipple stimulation therapy and 494 immediate synthetic oxytocin infusion without nipple stimulation) will be sufficient to detect a **10% absolute difference** (estimated 74% versus 64%) in spontaneous vaginal delivery with 90% power (alpha of 0.05).

Justification: At first glance, the anticipated 10% or greater absolute increase in the spontaneous vaginal delivery rate in our proposed trial appears modest. On the contrary, because the potential public health impact is large, this effect size is significant. It is estimated that 40% of the *one million* women who undergo inpatient labor induction each year in the U.S. are nulliparas. Therefore, a 10% increase in spontaneous vaginal delivery translates to 40,000 more spontaneous vaginal deliveries and *40,000 fewer operative deliveries each year*. Avoiding 40,000 operative deliveries each year will have substantial impact on overall morbidity and healthcare resource utilization in the U.S. and beyond.

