2) The sample size of 988 for the primary outcome will be sufficient to detect a 9.4% or 10.8% absolute difference in breastfeeding as the sole source of nutrition (BSSN) at the time of delivery hospitalization postpartum discharge with 80% power and 90% power, respectively (two-sided test, $\alpha=0.05$). This represents the difference between an expected BSSN rate of 47% in the setting of synthetic oxytocin infusion without nipple stimulation (average rate at the study sites based on institutional data) and 56.4% (with 80% power) or 57.8% (with 90% power) with nipple stimulation therapy.

3) Assuming a 15% attrition rate at 2 weeks postpartum (the time frame for our primary cost-effectiveness analysis in Aim 3), the sample size of 988 will have 90% power for detecting a standardized effect size of 0.22 for the between-group difference in cost and difference in quality adjusted life years (QALY) (two-sided test, $\alpha=0.05$). This is considered a small effect size based on conventional criteria, hence if we observe an even larger effect size, we should be sufficiently powered.

The sample size for this biospecimen trial is based on the primary comparison, specifically the difference in primary biomarkers from baseline to after 2 hours of treatment between patients performing nipple stimulation therapy and those receiving IV oxytocin. Sample size calculations are based on differences between non-laboring and laboring patients from prior reports (Table). Sample size was determined to achieve 80% power to detect a difference with a two-tailed alpha level of 0.05. The final sample size of 48 per exposure group is based on the largest sample size required (IL1beta). Therefore, there is more than adequate power for the remainder of the biomarkers of interest.

To detect a 10 mM difference in sodium concentration between the intrapartum nipple stimulation therapy group and the immediate synthetic oxytocin infusion group at 48 hours postpartum, with a standard deviation of 20 mM, 80% power, and a significance level of 0.05, a sample size of 32 participants per group is required. Accounting for an expected 30% dropout rate, we plan to recruit 46 participants per group.

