The primary comparison will be looking at milk composition before and after birth for participants in the nipple stimulation group. We will use Student's t-test to compare the paired milk samples from the same individuals.

Secondary comparison will be looking into milk composition between patients performing nipple stimulation therapy and those receiving IV oxytocin versus spontaneous labor at 12, 24, 48 and 72 hours postpartum. We will account for multiple measurements for each participant (if multiple samples will be collected) and those will be used for a mixed effect model. Structural equation model will be used for modeling the effect of additional variables (delivery mode, intentions to breastfeed, feeding frequency, maternal intention to feed etc.) on milk biomarkers and breastfeeding outcomes.

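### The milk sub-study needs about 64 evaluable participants per group for its stated comparison, not 32, so its stated 80% power is really about 50%

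*Protocol*

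**What the plan says.** Section 6.4.2 sets out the milk calculation in one sentence. It opens "To detect a 10 mM difference in sodium concentration between the intrapartum nipple stimulation therapy group"; the other arm is the one started on oxytocin at once, sodium is compared two days after birth, and the assumed SD is 20 mM. The conclusion drawn is "80% power, and a significance level of 0.05, a sample size of 32 participants per group is required". An expected 30% dropout raises this to 46 recruited per group. Section 5.3.1 repeats the calculation with the same result: "a sample size of 32 participants per group is required". The milk sentence does not say whether the test is one- or two-sided, but section 6.4.2 settles that in general: "All sample size and power estimates are based on two-tailed tests".

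The milk analysis plan in section 6.4.3.2 takes a different line: "The primary comparison will be looking at milk composition before and after birth for participants in the nipple stimulation group". That is a paired t-test in one arm. The comparison between arms becomes secondary and is worded to include spontaneous labor as well. On sampling, section 6.3 says "Postpartum milk samples will be collected from IV oxytocin and nipple stimulation treatments participants". Milk from before delivery is taken in the nipple stimulation arm only (sections 5.2.2 and 6.3).

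**The concern.** A difference of half a standard deviation between two independent groups is a familiar case, and 32 per group is about half the usual answer for 80% power. If the figure is wrong, the sub-study has roughly an even chance of finding the difference it says it is powered to find. A reader who relies on the stated 80% could then take a null result as evidence of no effect.

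The named primary comparison adds to the problem. The hypothesis in section 4.1 is that secretory activation comes earlier with nipple stimulation than with IV oxytocin alone, which is a contrast between arms. A before-and-after test in one arm cannot address it, because milk changes around birth whatever the method of induction. Section 3.2 itself places secretory activation at 48 to 72 hours postpartum in the usual course.

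**Working it through.** **Inputs** (sections 5.3.1, 6.4.2 and 6.1.2): difference δ = 10 mM; standard deviation σ = 20 mM, so δ/σ = 0.5; two-sided alpha 0.05 (z = 1.96); power 80% (z = 0.84); 1:1 allocation; 30% dropout.

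**Reproducing the protocol's figure.** The formula for one sample or for paired differences gives

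n = (1.96 + 0.84)² × (20/10)² = 31.4, rounded up to 32.

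This matches the protocol's number but is not the design described. The dropout step is correct: 32/0.7 = 45.7, so 46.

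**Two independent groups.** The variance of a difference between two means brings in a factor of 2:

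n per group = 2 × (1.96 + 0.84)² × (20/10)² = 62.8, so 63.

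The exact two-sample t-test gives 63.8, so 64. A one-sided test would still need 50 (normal) or 51 (t-test). No standard two-group version gives 32.

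**Power at the planned size.** With 32 per group the standard error of the difference is 20 × √(2/32) = 5 mM, so power ≈ Φ(10/5 − 1.96) = Φ(0.04) = 51.6%. Detectable differences use (1.96 + 0.84) times the standard error, for example 2.80 × 5 = 14.0 mM at 32 per group.

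| Evaluable per group | Power for 10 mM (t-test) | Difference detectable with 80% power (t-test) |
|---|---|---|
| 32 (46 recruited, 30% lost) | 50.4% | 14.2 mM |
| 46 (no losses) | 66.0% | 11.8 mM |
| 64 | 80.1% | 10 mM |

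To keep 80% power for 10 mM with 32 per group, the standard deviation would have to be about 14.3 mM rather than 20 mM. To support the claim as written with 30% dropout, recruitment would need 64/0.7 = 91.4, so 92 per group.

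**Check against the protocol's own biomarker table** (section 6.4.2). Only two rows are used.
- Oxytocin: difference 24.25, standard deviation 40.8, ratio 0.594, assigned 45 per group. The two-sample formula gives 44.4 (normal) or 45.4 (t-test), so the row follows it closely. The sodium ratio of 0.5 is smaller, so at the same power and alpha it cannot need fewer participants.
- Detectable difference at 48 per group: 23.6/40.8 = 0.578 for oxytocin and 13.3/23 = 0.578 for apolipoprotein E. On a standard deviation of 20 mM this is 0.578 × 20 = 11.6 mM. If 48 per group can detect only 11.6 mM, 32 per group cannot detect 10 mM.

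**Could adjustment rescue 32?** Covariate adjustment multiplies the required size by 1 − ρ². Going from 63 to 32 needs ρ² = 1 − 32/63 = 0.492, so ρ ≈ 0.70. No correlation or covariate is stated. A pre-delivery milk baseline could not supply one, because it exists in one arm only.

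**Comparisons set side by side.**
- Sized (5.3.1, 6.4.2): between arms, sodium, 48 hours.
- Hypothesised (4.1): between arms.
- Named primary (6.4.3.2): within the nipple stimulation arm, before against after birth.
- Added to the secondary comparison (6.4.3.2): spontaneous labor. The eligibility criteria for those controls (5.3.2) and the specimen procedures (6.3) cover blood and urine, and postpartum milk comes from the two randomised arms only.

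**The case against.** The arithmetic has no good defence: both statements say per group, both name the two randomised arms, and even a one-sided test needs 51. The fair objections concern weight and framing.

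- **Weight.** Milk sodium is an exploratory sub-study outcome. The 988 participants and the primary outcome of spontaneous vaginal delivery are unaffected, and no one's care depends on this figure. That stands and limits the reach of the finding, but it does not make the power statement true.
- **Cause.** A paired formula is only one possible source. A total of 64 read as 32 per arm would fit as well, and a paired t-test would need 34 rather than 32. The protocol does not say, so the origin is inference; the mismatch is not.
- **Before-and-after comparison.** Section 4.3 lists it as part of objective 7, with the descriptive purpose of seeing how milk changes. That also stands, and it is a reason to keep the analysis. It does not justify labelling it primary when the sample size and the hypothesis rest on the contrast between arms.
- **Matching power to analysis.** The 14 mM figure comes from a t-test at 48 hours, not from a mixed model. The 48-hour contrast from such a model should have about the same power or better, so the figure is a reasonable statement. No within-person correlation is given from which to claim more.

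**Conclusion.** The concern holds. On the stated inputs the sub-study needs 64 evaluable participants per group (63 by the normal approximation), twice the 32 given in sections 5.3.1 and 6.4.2. Power for 10 mM is about 50% at 32 per group and 66% if nobody is lost, and 80% power is reached only for about 14 mM. This rests on the protocol's own standard deviation of 20 mM, a two-sided 5% test, equal groups and no covariate adjustment, since none is described. Separately, section 6.4.3.2 names as primary a comparison that is neither the one sized nor the one hypothesised, and it includes a spontaneous-labor milk comparison that has no data. All of this is confined to the milk sub-study, but there the power statement has to be corrected.

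**What to change.** 1. In sections 5.3.1 and 6.4.2, keep the target of 46 recruited per group and restate what it supports: with 32 evaluable per group, 80% power for a difference of about 14 mM and about 50% power for 10 mM, at a standard deviation of 20 mM and two-sided alpha 0.05.
2. In section 6.4.3.2, make the sodium difference between the randomised arms at 48 hours the primary milk comparison, estimated from the planned mixed model over 12, 24 and 48 hours. The 72-hour samples, taken only from mothers still in hospital, can stay supportive.
3. Keep the before-and-after comparison in the nipple stimulation arm as a descriptive analysis, in line with objective 7.
4. Delete the spontaneous-labor comparison for milk.

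The cost is protocol wording and a less favourable power statement, with no extra patients, samples or procedures. If the sponsor prefers to keep the 10 mM claim at 80% power, the price is 92 recruited per group instead of 46, that is 46 more in each group.

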6.4.3 Planned Analyses

6.4.3.1 Primary Analyses

1) Overview: Data analyses will adhere closely to the CONSORT guidelines. Analyses will follow the intention-to-treat principle in which subjects will be analyzed in the group to which they were randomized, regardless of whether or not they received the assigned intervention.

2) Primary Analyses:

Descriptive statistics will characterize the group of individuals recruited and investigate comparability of the two study groups at baseline. Formal statistical testing will be limited to select baseline characteristics considered to be prognostic factors for the primary outcome including hospital admission body mass index (BMI), primary indication for labor induction, Bishop score at randomization, and birth weight. Categorical variables will be compared between trial groups by using the Chi-squared or Fisher's exact tests as appropriate, and continuous variables will be compared using Student's t-test or Wilcoxon Rank Sum Test, as appropriate. Distributions of continuous variables will be assessed by visual inspection of histograms.

The primary outcome (spontaneous vaginal delivery) and other categorical secondary outcomes will be compared between trial groups using Chi-square or Fisher's exact tests as appropriate. The estimates of the relative risk and 95% confidence intervals (95% CI) associated with the primary and secondary outcomes will be calculated using Agresti and Coull method. The time to event regression analyses for labor length (regardless of delivery mode) and labor length censored for cesarean will be evaluated by Kaplan-Meier estimates and plots, and tested with the log-rank test, whereas Cox proportional hazards analysis will be used in adjusted analyses accounting for Bishop scores at study entry (proportionality assumption will be checked graphically with $\ln(-\ln\text{Survival})$ plots), and results summarized using hazard ratios (HR) and 95% CI). A sensitivity analysis will be performed using the induction method that the patient actually received (per-protocol analysis) to determine whether crossovers influenced the results. The distribution of maximal percent newborn weight loss is not expected to follow a normal distribution in the population, so we plan to use Wilcoxon Rank Sum Tests to compare the distribution of the maximal percent weight loss between treatment groups, and summarize the results as medians (25th and 75th percentiles) and bootstrapped 95% CIs. Similarly, the distributions of the PIMS survey scores and MBFES survey scores are not expected to follow normal distributions in the population, so we will use Wilcoxon Rank Sum Tests to compare the distribution of the MBFES scores between treatment groups and summarize the results using the group medians (25th and 75th percentiles) and bootstrapped 95% CIs.

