6.1.2 Method of Assignment/Randomization

Enrolled subjects will be randomly assigned in a 1:1 ratio to both study groups. A web-based randomization sequence will be prepared using blocks of variable sizes, stratified by study site and amniotic membrane status (intact versus ruptured), and maintained centrally by the study statistician. The advantage of this method is that it provides a good probability of balance, and future assignments are unpredictable. A subject's group assignment will be obtained only after the subject is confirmed to continue to meet inclusion criteria, and a study number is entered and locked in using *REDCap* (Research Electronic Data Capture), an established, secure, web-based capture and management tool developed at Vanderbilt University. Although blinding of both subjects and their obstetrical clinicians would be ideal, blinding is clearly not possible in this trial. We will minimize systematic bias by applying the

same standard procedures for other labor and management strategies between groups at each study site. Further, the group assignment of subject will not be taken into account by trained study staff collecting maternal and neonatal outcomes. Importantly, the main study outcomes of spontaneous vaginal delivery and breastfeeding as the sole source of infant nutrition at hospital discharge are objective measures.

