My name is [Name] and I am a [insert job title] at Yale University and part of the research team for the STIM Study. I spoke with your doctor/midwife, and we believe you may be eligible to participate in this free and confidential research study investigating two different methods of labor induction. One method involves nipple stimulation using a breast pump and the other uses intravenous oxytocin infusion according to standard of care and hospital protocol. If you enroll, you will also be asked to complete brief surveys at 5 different times. You will be compensated [\$X] each time you do a survey, for a total of [\$X]. If you're interested in learning more, please reply to this message or call [insert phone]. We will also be available to answer any questions while you are at Labor & Birth at Yale New Haven Hospital. If you choose not to participate, you will continue with your usual care from your doctor/midwife. Thank you for your time.

Sincerely,

[Name]

- Inclusion/exclusion criteria will be reviewed with the patient's chart and/or discussion with the patient's responsible physician or midwife prior to approaching the patient to ensure that she meets eligibility criteria.
- If a patient appears to meet criteria for the trial, she will be told about the study and asked for written informed consent to participate in the trial. Consent will be obtained from a trained research team member.

2. Baseline Procedures

In addition to information collected for eligibility, the following information will be obtained at randomization from a subject interview followed by a review of her chart:

- Indication for labor induction
- Demographic information
- Medical history
- Obstetrical history including outcome(s) of any prior pregnancies (e.g., ectopic pregnancy, spontaneous or elective abortion prior to 20 weeks of gestation)
- Social history
- Current pregnancy complications (e.g., hypertensive disorders of pregnancy, gestational diabetes, etc.)

- Estimated fetal weight based on ultrasound (if within 2 weeks of randomization) or Leopold maneuvers
- Group B Streptococcus carrier status

3. Study Interventions

Women randomized to nipple stimulation will undergo the following procedures (intervention arm):

- Nipple stimulation will be done in the hospital after subjects receive proper training, and under the direction of the study and nursing teams.

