6.4.3.2 Secondary Objectives Analyses

Adjusted Analyses and Planned Subgroup Analyses

We will perform other analyses as needed aimed at obtaining adjusted assessments of treatment effectiveness, adjusting for baseline patient characteristics (covariates). The objectives of these analyses are to estimate the influence of covariates on the outcome and to use covariates to improve the estimated difference between treatment groups. The Poisson regression model (link=log) with robust standard errors stratified by study site will be used to identify and estimate the effect of multiple prognostic factors on the probability of spontaneous vaginal delivery and other categorical outcomes, with results summarized as adjusted risk ratios. For continuous secondary outcomes such as maximal newborn weight loss and PIMS and MBFES survey scores, quantile regression, e.g., modeling 50th percentile, will be considered to adjust for prognostic factors. Interaction tests will be used to determine whether the effectiveness of nipple stimulation therapy significantly differs across these subgroups. These analyses will be considered exploratory in nature and will not be viewed as providing confirmatory tests of hypotheses.

The following pre-specified subgroup analyses will be conducted:

1. Study site
2. Amniotic membrane status (intact versus ruptured) at enrollment
3. Presence versus absence of maternal diabetes (inclusive of pre-gestational and gestational diabetes)
4. Insurance type (commercial versus public insurance)
5. Maternal race (Black versus White versus Other)
6. Obesity (obese versus non-obese)

In separate models, each of these sub-group variables will be included as an additional covariate in the models for outcomes of interest, plus their interaction with treatment variable; followed by stratified analyses (by each of the above variables) of the effect of treatment on each outcome of interest.

Data Analysis Plan for the Biospecimen Sub-Study:

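### Factors the protocol itself calls prognostic stay out of the confirmatory comparison and are tested for baseline balance instead; birth weight is wrongly listed as a baseline factor

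*Protocol*

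**What the plan says.** Protocol section 6.4.3.1 opens with baseline comparability: "Formal statistical testing will be limited to select baseline characteristics considered to be prognostic factors for the primary outcome". It names four such factors: BMI at hospital admission, primary indication for induction, "Bishop score at randomization, and birth weight".

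The same section then fixes the primary comparison as a chi-square or Fisher's exact test of spontaneous vaginal delivery, with no covariates. It uses Bishop score at entry in one other place, an adjusted Cox model for labor length.

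Section 6.4.3.2, repeated in 6.4.4, plans robust Poisson models of spontaneous vaginal delivery on prognostic factors. One stated aim is a better estimate of the treatment difference. They are to be run where needed, the adjustment covariates are not listed, and their status is explicit: "These analyses will be considered exploratory in nature and will not be viewed as providing confirmatory tests of hypotheses".

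The baseline procedures in section 6.3 collect a pre-delivery measure of fetal size: "Estimated fetal weight based on ultrasound (if within 2 weeks of randomization) or Leopold maneuvers".

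**The concern.** After randomisation, any difference in a true baseline factor is due to chance. A p-value for that difference tests a hypothesis already known to be true, and it gives no guidance on whether to adjust. What a prognostic factor offers is precision when it enters the outcome model. The protocol names its prognostic factors, states that adjustment can improve the treatment estimate, and then withholds adjustment from its single confirmatory comparison.

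Birth weight raises a second point. It is unknown until delivery, which is when the primary outcome is settled. It cannot be a baseline characteristic, and it should not be in a list from which baseline covariates might later be drawn.

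At stake are some precision on the primary estimate, a baseline table that may show a spurious imbalance to explain, and a misclassified variable.

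**Working it through.** **Inputs (Protocol).** Section 6.4.2: "estimated 74% versus 64%) in spontaneous vaginal delivery with 90% power (alpha of 0.05"; "All sample size and power estimates are based on two-tailed tests"; 5% attrition; 494 women per arm. Section 6.1.2: "Enrolled subjects will be randomly assigned in a 1:1 ratio to both study groups". The share of outcome variance that the baseline factors explain (R²) is not in the document. It is an assumption here, shown as a range.

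**Step 1: reproduce the plan's sample size.** With p₁ = 0.64, p₂ = 0.74 and mean 0.69, the pooled-variance formula is

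n = [1.960·√(2·0.69·0.31) + 1.2816·√(0.64·0.36 + 0.74·0.26)]² / 0.10²
= [1.960·0.6541 + 1.2816·0.6502]² / 0.01 = 447.4 per arm.

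Continuity correction: n′ = (n/4)·[1 + √(1 + 4/(n·0.10))]² = 467.2, so 468 per arm. Attrition: 468/0.95 = 492.6, so 493 per arm or 986 in total, against 988 stated. The same method gives the other six rows of the table in section 6.4.2 exactly. The plan's figure is sound.

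**Step 2: power of the planned unadjusted test.** Evaluable women: 494 × 0.95 = 469.3, taken as 469 per arm. For the uncorrected chi-square:

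- standard error under the null = √(2·0.69·0.31/469) = 0.03020
- standard error under the alternative = √((0.64·0.36 + 0.74·0.26)/469) = 0.03002
- power = Φ[(0.10 − 1.960·0.03020)/0.03002] = Φ(1.359) = 91.3%.

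**Step 3: power with adjustment.** In a 1:1 trial, adjusting for baseline covariates multiplies the variance of the risk difference by about (1 − R²). Scaling both variances in step 2 gives:

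| Assumed R² | Power | Gain (points) | Equivalent sample, 1/(1 − R²) |
|---|---|---|---|
| 0% | 91.3% | – | 1.00 |
| 2% | 91.8% | +0.5 | 1.02 |
| 5% | 92.6% | +1.3 | 1.05 |
| 10% | 93.8% | +2.5 | 1.11 |
| 15% | 95.0% | +3.7 | 1.18 |

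**Step 4: check by simulation.** Each setting used 20,000 trials with 469 per arm, a logistic outcome with one normally distributed prognostic score, and marginal rates of 64% and 74%. The uncorrected chi-square was compared with a regression-adjusted risk difference using robust standard errors. Gains were +0.7 points at R² 2.7% (AUC 0.60), +1.1 at 5.2% (0.63), +2.2 at 9.4% (0.68) and +3.1 at 14.1% (0.72). This agrees with the formula, running slightly below it at the larger values.

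**Step 5: the balance tests.** If the four tests were independent and each run at 0.05, the chance of at least one significant result with no real difference would be 1 − 0.95⁴ = 18.5%. The protocol states no significance level for these tests and does not claim independence, so this is only an illustration.

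**The case against.** The strongest reply is that nothing is broken. An unadjusted chi-square is valid in a randomised trial, matches the two-proportion basis of the sample size, and exceeds the 90% target. Choosing an adjusted primary estimate is then a matter of efficiency, and a detailed covariate list commonly belongs in the SAP, which is not at hand. All of this stands. The point remains because the protocol is not silent here: it fixes the balance tests, the birth-weight label, the unadjusted primary test and the exploratory status of adjustment. An SAP that followed it would inherit all four.

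A reader might infer more than the text supports:

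- **That the factors are used for nothing but balance tests.** Bishop score enters the Cox model for labor length, and adjusted Poisson models of the primary outcome are planned as exploratory. The supportable statement is that none of the factors enters the confirmatory comparison.
- **That a definite number of power points is being given up.** The protocol gives no R² or AUC for these factors, and a weak set would gain half a point. The simulation also uses one error-free score in place of several imperfect clinical measures.
- **That birth weight will distort the treatment estimate.** It appears only in the balance list; no model names it as a covariate. Nor does any text let a balance test choose the main trial's primary analysis.

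A practical objection also stands in part. The protocol version is dated July 2025 and section 5.1.1 expects the last enrolment in June 2026, so a Bishop score missing for a woman already randomised may not be recoverable.

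**Conclusion.** The point holds as one of precision and classification. Admission BMI, induction indication and Bishop score are declared prognostic, tested for balance to no purpose, and left out of the confirmatory comparison. Birth weight is listed as baseline although it is known only after delivery. Neither the balance-test criticism nor the birth-weight correction depends on any power assumption.

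There is no power shortfall and no error in the sample size. The gain from adjustment is conditional: roughly half a point to just under four points over an assumed R² of 2% to 15%, equivalent to about 2% to 18% more women. It assumes 469 evaluable per arm, the planned rates, and covariates measured before randomisation. Adjustment for the randomisation strata is a separate question and is not counted here.

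**What to change.** In section 6.4.3.1:

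1. Delete the formal baseline tests and present balance descriptively.
2. In the baseline list, replace birth weight with estimated fetal weight at randomisation, which section 6.3 already collects.
3. Make the primary estimate a covariate-standardised risk ratio and risk difference with robust standard errors, using admission BMI, induction indication, Bishop score and estimated fetal weight at randomisation. Standardising keeps the target a marginal contrast between arms, as in the unadjusted comparison, so the intended change is in precision.
4. Keep the unadjusted chi-square as a supportive analysis, and align sections 6.4.3.2 and 6.4.4 so that this adjusted analysis is no longer labelled exploratory.

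Because the trial is open label and well into its enrolment period, the covariates and model should be fixed before outcome data are analysed by arm.

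The cost is wording and no extra participants, with one small downside. Bishop score is not named among the baseline items in section 6.3, and women with ruptured membranes qualify under section 5.3.2 whatever the cervical examination shows, so some scores may be missing. Simple imputation or a missing-value indicator would keep every randomised woman in the analysis. For women still to be enrolled, the score should be recorded before randomisation.
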